#### **3.4.4 Vital Signs, Weight, and BMI**

Vital signs will include heart rate, respiratory rate, body temperature, systolic and diastolic blood pressure and pulse pressure. Summary tables will be created to present the descriptive statistics for vital sign values, weight, and BMI as well as the change and percent change from baseline at each study visits.

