## PROTOCOL AMENDMENT

**Protocol Number:** ION-827359-CS2**Protocol Title:** A Double-Blind, Placebo-Controlled, Phase 2a Study to Assess the Safety, Tolerability, and Efficacy of ION-827359 in Patients with Mild to Moderate COPD with Chronic Bronchitis**Amendment Number:** 3**Amendment Date:** 2 February 2021

The major purpose of this amendment is to help prevent any potential bronchospasm after inhalation of Study Drug.

A list of changes to the protocol are below:

Protocol Section	Description of Change	Rationale
Section 6.1.3 Treatment Period	
The following is deleted from Table 1 (Withhold times for bronchodilators):
 
LABA (e.g., formoterol or salmeterol) 24 hours Ultra-LABA (e.g., indacaterol, vilanterol, or olodaterol) 36 hours LAMA (e.g., tiotropium, umeclidinium, aclidinium, or glycopyrronium) 36 – 48 hours
 
The following is added:
 
The usual dose of bronchodilators should not be taken the morning of the visit, until after spirometry is performed and prior to dosing (if applicable) with the study medication. Albuterol (salbutamol) 2 puffs, should be dosed prior to study drug both for in-clinic and at-home dosing.
	To help prevent any potential bronchospasm
Appendix A Schedule of Procedures	
Footnote 2 (vital signs) currently reads:
 
 BP, heart rate (HR), respiratory rate (RR), temperature
 
Will be amended to:
 
 BP, heart rate (HR), respiratory rate (RR), temperature, and pulse oximetry
	Correct an omission.
Appendix A Schedule of Procedures	
Footnote g added for spirometry on Day 1:
 
Perform spirometry (pre-Study Drug) pre and 20-30 minutes post albuterol dose (2 puffs) and then perform spirometry 1 and 2 hours post-Study Drug dosing.
	Collect baseline post-albuterol spirometry

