#### **10.6.2. Safety Analysis**

Treatment duration and amount of Study Drug (ION-827359 or placebo) received will be summarized by treatment group.

All treatment emergent AEs, all treatment emergent AEs potentially related to Study Drug, all treatment emergent serious AEs, and all treatment emergent serious AEs potentially related to

Study Drug (ION-827359 or placebo) will be summarized for each treatment group using the Medical Dictionary for Regulatory Activities (MedDRA™) coding system, by system organ class, preferred term, relationship to Study Drug, and severity. Narratives of deaths, SAEs, including early withdrawals from treatment and from study due to AE, will also be provided.

Laboratory tests to ensure subject safety including chemistry panel, complete blood count with differential, coagulation panel, etc., will be summarized by study visits for each treatment group. These safety variables will also be presented as change and percent change from Baseline over time after Study Drug administration, as appropriate.

Vital sign and ECG measures will be tabulated by treatment group. In addition, the number of patients who experience abnormalities in clinical laboratory evaluations will be summarized by treatment group.

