## Appendix A. Schedule of Procedures (Continued)

Study Week/Day	Screen	Run-in Period	Treatment Period (13 Weeks)								Post-Treatment Period (10 Weeks) +		
			W1 D1	W3 D15	W5 D29	W7 D43	W9 D57	W13 D85	W14 D92 (and Early Term)	W15 D99 	W18 D120	W24 D162	
Visit Window (Days)	NA	± 1	NA	± 2	± 3	± 3	± 3	± 2	± 5	± 5	± 5	± 5	
Scheduled Visit Number	1	2	3	4	5	6	7	8	9	9a	10	11	
HRCT scans 	X								X				
Adverse Events	X	X	X	X	X	X	X	X	X	X	X	X	
Concomitant Medications	X	X	X	X	X	X	X	X	X	X	X	X	
PK Blood Sampling 			X a, e	X a	X a		X a	X a, e	X	X	X	X	

Note: If not specifically labeled, "X" means anytime. S, Screening Day, D, Day, W, Week

\* Subjects that terminate early during the Post-Treatment Period should complete all procedures for Study Day 162

+ Post-Treatment Period visits can occur remotely, if necessary.

 Full physical exam to be given at Screening and abbreviated physical exam to be given during Treatment and Follow-up Period as indicated to assess changes from Screening

 BP, heart rate (HR), respiratory rate (RR), temperature, and pulse oximetry

 Women who are not surgically sterile

 For subjects in the bronchoscopy subgroup

 Fasting only for the screening lab. During this time the patient can drink water and they should ensure that they consume sufficient water in order to not become dehydrated

 If the platelet value, serum creatinine or liver enzyme tests are uninterpretable (e.g., due to clumping, hemolysis or quantity not sufficient) or missing a repeat blood specimen should be re-drawn as soon as possible (ideally within 7 days)

 If hematuria or 2+ proteinuria is observed, see confirmation guidance in Section 8.5

 Stored at -80 °C. Can be used for follow-up exploration of laboratory findings and/or AEs (e.g., measurement of cytokine and/or chemokine levels, measurement of additional markers of kidney function, measurement of antibodies, etc.) in this or subsequent clinical studies of ION-827359

 Urine test at Screening. Day 1 can be done at the site using established methods, e.g., a breathalyzer or urine test

 Height at Visit 1 only

 If time is not specified PK draw can be done anytime

 At-home dosing to occur on Days 8, 22, 36, 50, 64, 71, and 78 (± 1 day)

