### **Time (time is in reference to Study Drug (ION-827359 or placebo) administration):**

a Pre-dose

b Pre- and 20-30 minutes post-albuterol dose

c Pre-dose, and 2 hour

d Pre-dose, 1, and 2 hour

e For the subset of patients with full PK sampling; Pre-dose, 0.5, 1, 1.5, 2, 3, 4, 6, 8,12, 24 hours post-inhalation (window of  $\pm$  10% of the timepoint in minutes)

f In the morning, prior to study visit

g Perform spirometry (pre-Study Drug) pre and 20-30 minutes post albuterol dose (2 puffs) and then perform spirometry 1 and 2 hours post-Study Drug dosing.

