### 1.3.3 Safety Endpoints

- Incidence and severity of treatment-emergent adverse events (TEAE)
- Abnormal findings in laboratory assessments, electrocardiogram (ECGs), and vital signs

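### SAP 3.4.4 does not name pulse oximetry among the vital signs to be summarised, although the protocol counts it as one and says vital signs will be tabulated

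*Combined protocol and SAP*

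**What the plan says.** Protocol Appendix A, footnote 2, defines the vital signs to be taken: "BP, heart rate (HR), respiratory rate (RR), temperature, and pulse oximetry". Amendment 3, dated 2 February 2021, put pulse oximetry into that footnote, with the rationale "Correct an omission". Vital signs are scheduled at most clinic visits. On Day 1 and Day 85 the schedule adds footnote c, "Pre-dose, and 2 hour".

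Protocol 10.6.2 commits to the analysis without naming parameters: "Vital sign and ECG measures will be tabulated by treatment group". SAP 1.3.3 makes vital signs part of a safety endpoint: "Abnormal findings in laboratory assessments, electrocardiogram (ECGs), and vital signs".

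SAP 3.4.4 then gives its list: "Vital signs will include heart rate, respiratory rate, body temperature, systolic and diastolic blood pressure and pulse pressure". It goes on: "Summary tables will be created to present the descriptive statistics for vital sign values, weight, and BMI", with change and percent change from baseline at each visit. SAP 3.1.1 adds two general rules that apply here. All data are listed, and for data outside the efficacy and PD visit windows, several results under one visit label are averaged.

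**The concern.** The SAP list and the protocol definition differ by one item in each direction. A programmer who builds the vital-sign tables from SAP 3.4.4 has an instruction to produce pulse pressure and none to produce oxygen saturation. Saturation values would then be visible only patient by patient in listings, or indirectly if an investigator reported a fall as an adverse event.

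This matters because the drug is nebulised in patients with COPD, and abnormal vital-sign findings are a stated safety endpoint. With treatment terminated and efficacy reduced to description (SAP 3.3), the safety summaries are a main product of the study. A between-group shift in saturation is easier to see in a table by treatment group than in a listing.

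**Working it through.** No sample size, power or error rate enters this point, so the check is a comparison of texts with some date and count arithmetic.

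**1. The two lists side by side.**

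| Measure | Protocol Appendix A, footnote 2 | SAP 3.4.4 |
|---|---|---|
| Blood pressure | yes | yes (systolic, diastolic) |
| Heart rate | yes | yes |
| Respiratory rate | yes | yes |
| Temperature | yes | yes |
| Pulse oximetry | yes | not named |
| Pulse pressure | not listed | yes |

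Four of the five protocol measures carry over; pulse oximetry does not.

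**2. Is it covered elsewhere in the SAP?** No. Neither pulse oximetry nor oxygen saturation is mentioned in any other section.

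**3. Is the omission announced?** No. The SAP states its other reductions openly: the per-protocol and subgroup sets (3.1.2), the model-based analyses (3.3), HRCT (3.3.3.6) and exposure-response (3.5.2). Where it moves data to listings only, as for bronchial brushings and BAL (3.3.3.2, 3.3.3.3), it gives a reason. It says nothing about oximetry.

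**4. Did the SAP predate the amendment?** No. The SAP is dated 26 August 2021. From 2 February that is 26 + 31 + 30 + 31 + 30 + 31 + 26 = 205 days later.

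**5. How many patients could be affected?**
- Upper bound: 59 dosed (SAP 1.1).
- Completed Week 14: 10 (SAP 3.3), and 10/59 = 17%. Some others may have had a Day 85 reading without yet completing Week 14; that number is not given.
- Treatment stopped on 29 April 2021, which is 26 + 31 + 29 = 86 days after 2 February. Day 85 falls 84 days after Day 1, so a patient dosed on schedule could reach Day 85 by then only if first dosed by 4 February (6 February using the 2-day visit window). Patients with a Day 85 dose therefore started treatment before the amendment date or within days of it. Whether they have a Day 1 saturation to compare with depends on whether sites recorded oximetry before Amendment 3, which the documents do not say.

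**6. What else looks at the lungs after dosing?** Spirometry at 1 and 2 hours after study drug is scheduled on Day 1 and Day 57, with matching windows in SAP 3.1.1. SAP 3.3.1 tabulates the proportions of patients and of doses with an FEV1 fall above 20%. On Day 85, spirometry is scheduled only before and after albuterol, so the 2-hour vital signs are the scheduled respiratory check after that dose.

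**7. Would adding the name be enough?** Not if the pre-dose and 2-hour readings share a visit label, which the documents do not settle. On Day 1 the pre-dose value x is also the baseline. If saturation falls by d at 2 hours, the averaged value is (x + x − d)/2 = x − d/2, and the table shows a change of −d/2 instead of −d. Half the fall disappears.

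**The case against.** The case against treating this as more than a wording difference has real weight.

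- The SAP says vital signs will include the named items; it does not say only those. Since the SAP announces its other removals and protocol 10.6.2 still stands, a sponsor could tabulate oximetry without contradicting anything. A reader might infer that the SAP forbids or deliberately drops the table; the text does not support that. It does leave oximetry without an instruction.
- A reader might infer that respiratory safety after inhalation rests on listings and adverse event reports alone. That is not so, given the FEV1 tabulation in SAP 3.3.1. It does not, however, cover the time after the Day 85 dose.
- A reader might link oximetry to the bronchospasm purpose of Amendment 3. The amendment gives that reason for the bronchodilator change; for oximetry it says only that an omission was corrected.
- A reader might take pulse pressure to be a slip for pulse oximetry. That is plausible, but it is an inference. Pulse pressure can be derived from systolic and diastolic pressure and may be intended.
- With at most 59 patients, a listing can be read through, and no test or decision rule depends on this table.

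These points limit the size of the problem. They do not remove the mismatch, and none of them gives a reason for leaving out a measure that the protocol requires.

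**Conclusion.** The mismatch holds. Under SAP 3.4.4 as written, oxygen saturation is assigned to listings only, whereas footnote 2 and protocol 10.6.2 together place it in the tables by treatment group. The gap is in summary reporting, not in data collection.

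Its size cannot be stated as 59 patients. That is a ceiling; the number with usable readings is unknown, and Day 85 readings will be few, so Day 1 is likely to carry most of the post-dose information. The conclusion rests on reading the SAP list as the working specification for the tables. It does not depend on why pulse pressure appears there. The point is modest, but it leaves a stated safety endpoint incompletely summarised and is cheap to correct.

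**What to change.** In SAP 3.4.4, add oxygen saturation by pulse oximetry to the list. Pulse pressure may stay as a derived value. Summarise value and change from baseline by treatment group and visit; the baseline rule in SAP 3.1.1 for other assessments already serves. On Day 1 and Day 85, show the pre-dose and 2-hour readings separately and exempt them from averaging under a common visit label. Report the number of patients with a reading at each time point, so that the effect of Amendment 3 and of early termination is visible. A summary of the lowest post-baseline value per patient is optional. If the omission was intended, say so and give the reason, as the SAP does for its other reductions.

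The cost is one more parameter in an existing table and a time-point split at two visits. The data are already required by the protocol, and study conduct does not change.

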#### **3.4.5 Physical Examinations**

Adverse changes in physical examinations that are deemed clinically significant by the Investigator will be classified as adverse events. All physical examination data will be provided in a data listing.

#### **3.4.6 12-Lead Electrocardiograms (ECG)**

The ECG data will include heart rate, RR interval, PR interval, QRS Duration, QT interval, QTcF, QTcB, and overall interpretation.

For the continuous variables above, descriptive statistics of the results at each study visit, as well as the changes and percent changes from baseline to each study visit, will be summarized by treatment group. The average of triplicates will be used in the summary. For the categorical responses to overall interpretation, the counts and percentages will be tabulated by treatment group. The worst case result of triplicates will be used in the summary.

In addition to the descriptive summary, a shift analysis from baseline to the worst (highest) post-baseline QTcF and QTcB by treatment group will be conducted. The categories for the shift analysis will be:  $\leq 450$  msec,  $> 450$  msec to  $\leq 480$  msec,  $> 480$  msec to  $\leq 500$  msec, and  $> 500$  msec. The average of triplicates will be used to categorize the data.

The number and percent of patients experiencing an increase from baseline in QTcF and QTcB of greater than 30 msec or 60 msec at any time post-baseline will be summarized by treatment group. The average of triplicates will be used to determine the increase.

Only data collected from the central reader and provided by ERT will be included in the summary table. The local ECG data will only be listed if collected.

The ECG data will be presented in a subject listing.

### **3.4.7 Prior and Concomitant Medications**

Prior medications include medications started prior to the first dose of study medication regardless whether continued while on treatment or not. Concomitant medications include medications that patients are exposed to on or after the first dose of study medication. Partial or missing medication start date or end date will be imputed by the following imputation rules:

Start date:

- If year, month and day are all missing then assign the date of first dose of Study Drug
- If month and day are missing and year is:
  - earlier than the year of the first dose of Study Drug then assign December 31
  - otherwise, assign January 1
- If only day is missing and month-year is:
  - earlier than the month-year of the first dose of Study Drug then assign the last day of the month
  - otherwise, assign the first day of the month

End date: imputation will be performed for the end date only if the day or month is missing (i.e., year is present):

- If month and day are missing, then assign December 31
- If only day is missing, then assign the last day of the month

If the imputed start date is later than the imputed end date, then set the imputed start date to the imputed end date.

Prior and concomitant medications will be coded using WHO Drug dictionary and summarized by ATC class, preferred name and by treatment group and Part.

### **3.5 Pharmacokinetic Analysis**

For pharmacokinetic (PK) assessment, plasma trough PK samples during the 13-week treatment period and post-treatment samples during the 10-week post-treatment follow up period will be collected from all patients in the study. Additionally, extensive plasma PK

samples will be collected in the PK subgroup following the first (Day 1) and last (Day 85) inhalation administration.

PK analysis will be conducted for the PK Population only.

### **3.5.1 Plasma Concentration Data**

Plasma concentrations of ION-827359 over time, along with the scheduled (nominal) and actual samples times (i.e., time from the end of inhalation) will be listed (when applicable) for each subject, by treatment, group/subgroup, cohort, nominal dose, and day. In addition, percent differences between scheduled and actual sampling times will be listed for all subjects. Percent differences between actual administered dose and nominal dose will also be listed.

Plasma concentrations below the lower limit of quantification (LLOQ) will be indicated by “BLQ”. For the purpose of calculating typical descriptive statistics (n, mean, SD, %CV, geometric mean, geometric %CV, median, minimum, and maximum) for plasma concentrations, all BLQ values will be set to zero. Mean plasma concentrations that are BLQ will be presented as BLQ, and the corresponding SD, %CV, geometric mean, geometric %CV will be reported as not applicable. Summary statistics of the ION-827359 plasma concentrations will be tabulated by treatment, group/subgroup, cohort, nominal dose, day, and scheduled time point. At the discretion of the pharmacokineticist and/or biostatistician, samples may be excluded from descriptive statistics if there are large deviations between scheduled and actual sampling times, or large deviations between actual dose and nominal dose.

ION-827359 plasma concentration versus time (actual) profiles (up to 24 hours post dose and/or full profiles) following the dose on Days 1 and 85 for each subject in the PK subgroup and received ION-827359 active treatment, as well as the median plasma concentrations versus time (scheduled) profiles, will be presented graphically on linear and semilogarithmic scales. At the discretion of the pharmacokineticist and/or biostatistician, samples may be excluded from the median plots if there are large deviations between scheduled and actual sampling times.

### **3.5.2 Plasma Pharmacokinetic Parameters**

Non-compartmental pharmacokinetic analysis of ION-827359 will be carried out on each individual subject data set where full PK sampling profiles are collected (PK subgroup) using Phoenix WinNonlin version 8.0 or higher (Pharsight Corporation, Mountain View, CA). Plasma pharmacokinetic parameters in each subject (when applicable) will be determined. For calculation of PK parameters, all BLQ values will be set to zero. The following plasma PK parameters for ION-827359 will be calculated (when applicable and not necessarily limited to) and based on actual sampling times:

- $C_{\max}$ : the maximum observed ION-827359 concentration in plasma
- $T_{\max}$ : the time at which  $C_{\max}$  occurs

- AUC0-24h: areas under the plasma concentration-time curve from time zero (pre-dose) to 24 hours will be calculated using the linear up-log down trapezoidal rule following the dose on Day 1 and Day 85
- AUC0-168h (AUCτ): partial area under the plasma concentration-time curve (AUC) from time zero to 168 hours will be calculated using the linear up-log down trapezoidal rule following the dose on Day 85
- CLss/F: Apparent plasma clearance at steady-state after inhalation administration. This parameter will be calculated as CLss/F = Actual Dose/AUCτ following the dose on Day 85
- t1/2λz: apparent terminal elimination half-life will be calculated from the equation,  $t_{1/2\lambda z} = 0.693/\lambda_z$ , where  $\lambda_z$  is the rate constant associated with the apparent terminal elimination phase. This parameter will be calculated following the dose on Day 85.
- Vz/F (L): Apparent volume of distribution in the terminal phase will be calculated from  $V_z/F = \text{Actual Dose}/(AUC_\tau \times \lambda z)$  following the dose on Day 85.

$\lambda_z$  shall be determined over a span equal to at least  $1.5 \times t_{1/2\lambda z}$ . A minimum of three data points in the elimination phase will be used to calculate  $\lambda_z$  using log-linear regression analysis and the adjusted correlation of determination values ( $r^2_{\text{adj}}$ ) shall be at or greater than 0.8 for the estimate to be accepted. If at least one of these three conditions are not fulfilled, the PK parameters depending on  $\lambda_z$  (i.e.,  $t_{1/2\lambda z}$  and  $V_z/F$ ) shall be flagged as not reliable if calculated and listed. They will generally be excluded from descriptive statistics and statistical testing procedures, or at the discretion of the pharmacokineticist, who is in charge of the PK analysis.

Plasma pharmacokinetic parameters will be summarized using descriptive statistics (n, mean, SD, %CV, geometric mean, geometric %CV, median, minimum, and maximum) by cohort, nominal dose, and day.

Exposure-response relationships will not be conducted due to the early termination of the study.

Version:	1
Version Date:	26 Aug 2021
Title:	

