## 1.1 Study Overview

This is a Phase 2a, double blind, randomized, placebo-controlled, dose-ranging study, will be conducted at multiple centers in Europe. Patients with CB associated with COPD will be randomized to ION-827359 or matching placebo administered by oral inhalation once weekly for 13 weeks.

Approximately 180 patients are planned to be enrolled in this study. Patients will be randomized in a 2:2:1:1 ratio to the following 4 treatment groups respectively:

- ION-827359 37.5 mg (1.5 mL) once per week
- ION-827359 75mg (3 mL) once per week
- Placebo (1.5 mL) once per week
- Placebo (3 mL) once per week

There are 3 subset studies:

1. A subset of up to about 24 patients will have PK profile sampling performed after the first and last dose
2. A subset of up to about 60 patients will have low dose inspiratory and expiratory HRCT scans to assess regional lung ventilation performed before and post-treatment
3. A subset of up to about 18 patients will undergo bronchoscopy and BAL for target engagement and inflammatory biomarkers before and post-treatment

A patient may be enrolled in a maximum of 1 subset study.

The study will consist of Screening, Treatment, and Post-Treatment Periods. Please refer to the Schedule of Procedures in protocol Appendix A. The study for an individual patient will generally consist of the following Periods:

- A  $\leq$  4-week Screening Period. The last week of which is the Run-in Period
- A 13-week Treatment Period during which study medication (ION-827359 or placebo) will be administered by nebulization once per week (both in-clinic and at home dosing)
- A 10-week Post-Treatment Period

Patients may be required to attend additional visits for monitoring of AEs or abnormal investigation results. The frequency of additional monitoring will be determined by the Sponsor Medical Monitor in consultation with the Investigator.

Due to a combination of findings in a recently completed chronic toxicology study in non-human primates and the totality of the data collected to date in this and other studies of ENaC inhibition, the study treatment has been terminated on April 29th, 2021, after 60 patients have been randomized and 59 patients have been dosed. All patients who were on treatment at the time of study treatment termination will stop the treatment, continue in the study to complete the early termination visit (Week 14 Day 92) and the 10-week Post-Treatment period.

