## 2.2 Randomization & Treatment Allocation

Patients will be randomized, after all Baseline and Screening assessments have been completed and after the Investigator has verified that they are eligible per criteria in protocol Sections 5.1 and 5.2.

No subject may begin treatment prior to randomization and assignment of a unique subject identification number.

Eligible patients will be randomized using an Interactive Voice/Web-Response System (IXRS) in a 2:2:1:1 ratio to receive ION-827359 37.5 mg (1.5 mL), ION-827359 75 mg (3 mL), Placebo 1.5 mL, and Placebo 3 mL, respectively. Cohort A will be defined as those subjects receiving 1.5 mL of Study Drug or placebo, and Cohort B as those receiving 3 mL of Study Drug or placebo. These cohorts will run concurrently.

There will be 4 separate and independent randomizations:

- PK subgroup: approximately 24 patients
- HRCT subgroup: approximately 60 patients
- Bronchoscopy subgroup: approximately 18 patients
- Other: patients who are not in the above 3 subgroups, approximately 78

Randomization information will be concealed from the Investigators and patients until the end of the study, with the exception of an emergency situation involving a patient that requires unblinding of the treatment assignment.

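### SAP 3.5.2 plans terminal half-life only after the Day 85 dose, leaving out washout samples from PK-subgroup patients whose treatment was stopped earlier

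*Combined protocol and SAP*

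**What the plan says.** SAP 3.5.2 restricts the parameter analysis by population and half-life by dose.

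- Population: "Non-compartmental pharmacokinetic analysis of ION-827359 will be carried out on each individual subject data set where full PK sampling profiles are collected (PK subgroup").
- Dose: "This parameter will be calculated following the dose on Day 85". AUC over the dosing interval, CLss/F and Vz/F carry the same Day 85 condition.

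The parameter list is introduced as "when applicable and not necessarily limited to", so it is not closed. For lambda-z the SAP sets three conditions: "A minimum of three data points in the elimination phase will be used to calculate" it, the span must be at least 1.5 half-lives, and adjusted r2 must be at least 0.8.

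On sampling, SAP 3.5 says that "post-treatment samples during the 10-week post-treatment follow up period will be collected from all patients in the study". Protocol Appendix C places these samples at Day 92 or early termination, Day 120 and Day 162 for everyone, with Day 99 added in the PK subgroup. On termination, SAP 1.1 says: "All patients who were on treatment at the time of study treatment termination will stop the treatment, continue in the study", through the early termination visit and the 10-week follow-up.

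Protocol 10.6.4 also confines plasma PK assessment to the PK subgroup, but has half-life calculated where the data allow, without naming a dose day.

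**The concern.** The Day 85 condition suits a trial in which patients complete 13 weekly doses. This SAP is dated 26 August 2021, about four months after treatment was terminated on 29 April 2021. Other sections were adapted: the per-protocol set was removed, the models were dropped, BAL and bronchial brushing data are only listed, and the HRCT and exposure-response work was abandoned. The half-life condition stayed, and no rule covers patients whose last dose came before Day 85.

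Pharmacokinetics is a secondary objective and endpoint, and a half-life describes how long drug remains measurable in plasma after dosing stops. Followed as written, the plan could give a half-life from very few patients, possibly none at one dose level, while scheduled washout samples from other PK-subgroup patients appear only in the concentration listings and summaries of SAP 3.5.1.

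**Working it through.** The plan states no evaluable number for half-life, so there is no figure to reproduce. The check is a count.

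**Inputs**
- Dosed: 59 (SAP 1.1). Completed Week 14, all arms and subgroups: 10 (SAP 3.3).
- Allocation 2:2:1:1 (SAP 2.2), so 4/6 receive active drug.
- "PK subgroup: approximately 24 patients" of about 180 planned (SAP 2.2). No patient had entered the HRCT subgroup of about 60 (SAP 2.5.5).
- The PK-subgroup share among enrolled patients is not given. Assumed values: 24/180 (as planned), 24/120 (without HRCT) and 24/60 (all PK places filled among the 60 randomized).

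**Planned.** Active PK-subgroup patients: 24 × 4/6 = 16.

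**Evaluable under the Day 85 condition.** This takes the 10 Week 14 completers as those given the Day 85 dose. Expected number = 10 × 4/6 × share. The chance of none is (1 − 4/6 × share)^10, treating patients as independent.

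| Assumed share | Expected, both doses | Per dose level | Chance of none |
|---|---|---|---|
| 24/180 | 0.9 | 0.4 | 39% |
| 24/120 | 1.3 | 0.7 | 24% |
| 24/60 | 2.7 | 1.3 | 4% |

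The ceiling is about 10 (all completers active and in the PK subgroup), plus anyone who took the Day 85 dose but had not reached Week 14. The figure 10 × 4/6 = 6.7 is the expected number of active completers, not a limit.

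**What dropping the condition adds within the PK subgroup.** The other 59 − 10 = 49 patients give 49 × 4/6 = 32.7 active. Multiplying by the three shares gives about 4.4, 6.5 and 13.1 further PK-subgroup candidates, before any fail the acceptance criteria.

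**Can washout samples meet the criteria?** None of the three criteria requires a Day 85 dose or a 0 to 24 hour profile. This assumes that the spacing of the visits is kept after early termination.
- Day 92 to Day 162 spans 70 days; 70/1.5 = 46.7, so half-lives up to about 47 days can satisfy the span rule.
- A PK-subgroup patient has four washout samples. If Day 162 is not quantifiable, Days 92, 99 and 120 remain: 28 days, and 28/1.5 = 18.7 days.
- Outside the subgroup there are exactly three samples, so all must be quantifiable and in the elimination phase. With n = 3, adjusted r2 = 1 − 2(1 − r2), so 0.8 requires r2 of at least 0.90.

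**Pool if all active patients are considered.** 59 × 4/6 = 39.3, so about 39 at most.

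**The case against.** A reader might infer that termination left the SAP discarding half-life data from about 39 patients. The documents do not support that. The PK-subgroup limit comes from protocol 10.6.4 and would have applied in a completed trial; only the Day 85 condition is out of step with termination. The figure of 39 is a ceiling: the documents give no quantification limit or expected half-life, post-treatment visits may be remote, and values below quantification are set to zero and cannot enter a log-linear fit.

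A reader might also infer that half-life will certainly rest on one or two patients. That is not established either. Protocol 4.2 assigns subgroups by site, so the share among early enrolees could differ widely from the planned one.

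It can further be argued that nothing is forbidden. The SAP list is open, the protocol leaves additional parameters to the PK scientist, and every concentration is listed with actual times. That is true, but permission is not a plan: no population, starting dose or reporting rule is set for patients stopped early.

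Finally, SAP 1.1 names a chronic toxicology finding among the reasons for stopping but does not connect it to plasma persistence, so the case for the change should not rest on that link. No primary, safety or inferential conclusion depends on this parameter.

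**Conclusion.** The point stands for the Day 85 condition. It was kept in a SAP written when 10 of 59 dosed patients had completed Week 14, and it is narrower than the protocol on timing. It leaves scheduled, potentially usable washout data from active PK-subgroup patients out of the planned half-life analysis. The expected evaluable number is about 0.9 to 2.7 over two dose levels against 16 planned. That range rests on the assumed subgroup shares, on completers being spread across arms in the allocation ratio, and on Week 14 completion standing in for receipt of the Day 85 dose.

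Extending half-life to active patients outside the PK subgroup is a separate and weaker step: it goes beyond the population the protocol planned, and its yield is unknown.

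**What to change.** Amend SAP 3.5.2 as follows.

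- In all active PK-subgroup patients, calculate lambda-z and half-life from the actual last dose, whatever its day, using actual times and the three existing acceptance criteria.
- Report by dose level, with the number evaluable and the number of doses received, since patients will have stopped after different numbers of doses.
- As a supplementary analysis, apply the same rule to other active patients with three quantifiable samples after the last dose. State that each such estimate rests on three points, and that requiring quantifiable late samples favours patients with longer half-lives.
- Keep AUC over the dosing interval, CLss/F and Vz/F restricted to Day 85 profiles.

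The cost is SAP wording and additional analysis of samples already scheduled; no new visit or sample is needed. The drawback is lower precision per patient, and some estimates will fail the criteria.
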